#### 7.4.7. Improvement ≥3 dB shifts in median Spearman-Kärber estimates

- *Computation of the Endpoint*

Improvement ≥ 3 dB shifts in median Spearman-Kärber estimates at each post-baseline visit for treated ears will be computed as 1 if the post-baseline Spearman-Kärber estimate – baseline Spearman-Kärber estimate is ≥3 and as 0, otherwise where the baseline and post-baseline Spearman-Kärber estimates are not missing.

- *Analysis of the Endpoint*

The incidence of improvement ≥3 dB shifts in median Spearman-Kärber estimates at each post-baseline visit for treated ears will be summarized using frequencies and percentages by visit and treatment group for subjects in the FAS.

Treatment group comparisons may be performed using the approach described in Section 7.4.5 for subjects in the FAS.

- *Sensitivity Analyses of the Endpoint*

The analyses will be repeated for subjects in the PPAS.

#### 7.4.8. Incidence of incorrect phonemes

- *Computation of the Endpoint*

For each unique phoneme, the percentage not recognized correctly over all signal-to-noise ratios will be computed by subject, visit, and ear.

Post hoc endpoints may be derived for phonemes not recognized correctly at each signal-to-noise ratio.

- *Analysis of the Endpoint*

Heat maps will be produced for the percentage of phonemes not recognized correctly by visit and treatment group for treated ears using the same approach described in Section 7.3.11.

Heat maps at each signal-to-noise ratio may also be produced post-hoc. Additional post hoc analyses may be produced on select unique phonemes of interest, based on the final results in the heat map described above. The post hoc analyses may include heat maps by visit for treated ears also taking into account the location of the phoneme within the word (phoneme/location) for subjects in the FAS. Post hoc treatment group comparisons may also be performed.

- *Sensitivity Analyses of the Endpoint*

None.

#### 7.5. Pure Tone Audiometry

The pure tone audiometry test will be used to determine a subject's threshold for hearing at the following frequencies transmitted via air and bone: air tested at 0.25, 0.5, 1, 2, 3, 4, 6 and 8 kHz; and bone tested at 0.5, 1, 2, 3 and 4 kHz. If both masked and unmasked results are available for the same visit, date, ear, and frequency, the masked results will be used for analysis. This test will be performed at Screening, Day 15, 60, 90, 150, and 210.

Baseline scores for analysis will be computed from the Screening visit. For measurements post-Screening, missing response values for a given frequency, with classification of "NR" (no response due to subject audiometric thresholds greater than the maximal calibrated dB of the equipment), will be imputed using the maximum dB for the audiometry equipment of a given site plus 5 dB and classified as no signal at that frequency. Missing response values at Screening will remain missing.

### 7.5.1. Air and Bone Conduction audiometry dB hearing thresholds by frequency

- *Computation of the Endpoint*

At each visit and by ear (left, right), the AC and BC audiometry dB hearing thresholds will be recorded for each frequency (Air: 0.25, 0.5, 1, 2, 3, 4, 6, and 8 kHz; Bone: 0.5, 1, 2, 3, and 4 kHz). Left and right ears will be mapped to treated and untreated for analysis, as described in Section 3. Missing values will be imputed per Section 7.5.

- *Analysis of the Endpoint*

Separately for AC and BC, the hearing threshold at each frequency will be summarized descriptively for treated and untreated ears separately by visit and treatment group for subjects in the FAS.

In treated ears only for subjects in the FAS, treatment group comparisons for AC hearing threshold at each frequency will be analyzed using separate mixed-effect, repeated measures models using fixed covariates for treatment group, WR score at baseline (<50% versus  $\geq$ 50%), etiology of hearing loss (SSNHL versus NIHL), visit, and interaction between visit and treatment group. The covariance structure (UN or AR(1)) that provides the best model fit for the PTA, as described in Section 7.5.5, will be implemented with a repeated statement in SAS. The treatment group differences analyzed will be between each FX-322 group (including the pooled FX-322 group) versus placebo, and comparisons between the individual FX-322 groups (excluding the pooled FX-322 group). Comparisons will be made by visit (e.g., estimated LS Mean differences by visit) and overall (e.g., Type III Sums of Squares) for each frequency. The analysis will be repeated for BC hearing thresholds.

A scatter plot of the mean AC audiometry thresholds by frequency will be prepared for treated and untreated ears for each treatment group with lines connecting each point.

- *Sensitivity Analyses of the Endpoint*

The analyses will be repeated for subjects in the PPAS.

If there are any dosing administrations errors such that a not qualified ear is treated, the descriptive summaries by treated and untreated ears will be repeated for subjects in the FAS including all treated and untreated ear data.

### 7.5.2. AC and BC Improvement $\geq$ 10 dB from baseline for two contiguous frequencies

- *Computation of the Endpoint*

AC Improvement  $\geq$ 10 dB from baseline for two contiguous frequencies at each post-baseline visit for treated ears will be computed as 1 if the post-baseline threshold – baseline threshold is  $\geq$ 10 dB for two contiguous frequencies and as 0, otherwise. The endpoint will utilize imputed values per Section 7.5. The BC Improvement  $\geq$ 10 dB will be derived using the same approach.

- *Analysis of the Endpoint*

The incidence of AC improvement  $\geq 10$  dB from baseline for two contiguous frequencies at each post-baseline visit for treated ears will be summarized using frequencies and percentages by visit and treatment group for subjects in the FAS. The summary will be repeated for BC improvement.

In treated ears only for subjects in the FAS, treatment group comparisons for incidence of AC improvement  $\geq 10$  dB from baseline for two contiguous frequencies may be analyzed using a generalized estimating equation based on the binomial distribution with logit link. The fixed covariates may include treatment group, WR score at baseline (<50% versus  $\geq 50\%$ ), etiology of hearing loss (SSNHL versus NIHL), visit, and interaction between visit and treatment group. Covariates for WR score at baseline and etiology of hearing loss may be dropped if the model fails to converge. A random effect for within-subject, repeated measures variability may be included. The treatment group differences analyzed will be between each FX-322 group (including the pooled FX-322 group) versus placebo, and comparisons between the individual FX-322 groups (excluding the pooled FX-322 group). Odds ratios, 95% CIs, and p-values may be reported and comparisons will be made by visit and overall. The analysis will be repeated for BC improvement.

- *Sensitivity Analyses of the Endpoint*

The analyses will be repeated for subjects in the PPAS.

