### 7.5.3. AC and BC Improvement $\geq 15$ dB from baseline for any frequency

- *Computation of the Endpoint*

AC Improvement  $\geq 15$  dB from baseline for any frequency at each post-baseline visit for treated ears will be computed as 1 if the post-baseline threshold – baseline threshold is  $\geq 15$  dB for any frequency and as 0, otherwise. The endpoint will utilize imputed values per Section 7.5. The BC Improvement  $\geq 15$  dB will be derived using the same approach.

- *Analysis of the Endpoint*

The incidence of AC improvement  $\geq 15$  dB from baseline for any frequency at each post-baseline visit for treated ears will be summarized using the approach described in Section 7.5.2 for subjects in the FAS. The summary will be repeated for BC improvement.

Treatment group comparisons for AC improvement and BC improvement may be performed using the approach described in Section 7.5.2 for subjects in the FAS.

- *Sensitivity Analyses of the Endpoint*

The analyses will be repeated for subjects in the PPAS.

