### 7.5.9. Composite WR, WIN and Pure Tone Audiometry Endpoint

- *Computation of the Endpoint*

The composite endpoint will be assessed in treated ears and defined as simultaneously meeting both of the following conditions at any visit (Day 90 or 210):

- A post-baseline  $\geq 10\%$  WR improvement OR a  $\geq 10\%$  WIN improvement, and
- A post-baseline 10 dB improvement in 2 contiguous frequencies or a post-baseline 15 dB improvement in any frequency for AC thresholds

Post-baseline  $\geq 10\%$  WR improvement is defined in Section 7.3.5 and  $\geq 10\%$  WIN improvement is defined in Section 7.4.5. Post-baseline  $\geq 10$  dB improvement in 2 contiguous frequencies for AC thresholds is defined in Section 7.5.2 and post-baseline  $\geq 15$  dB in any frequency for AC thresholds is defined in Section 7.5.3.

The composite endpoint will be computed as 1 if both conditions are met in the treated ear at the same visit for any of the post-baseline visits (Day 90 and 210) and as 0, otherwise.

- *Analysis of the Endpoint*

The incidence of the composite WR, WIN and pure tone audiometry endpoint for treated ears will be summarized using frequencies and percentages by treatment group for subjects in the FAS.

In treated ears only for subjects in the FAS, treatment group comparisons for the composite endpoint will be analyzed using a logistic regression model. The fixed covariates will include treatment group, WR score at baseline ( $< 50\%$  versus  $\geq 50\%$ ), and etiology of hearing loss (SSNHL versus NIHL). The treatment group differences analyzed will be between each FX-322 group (including the pooled FX-322 group) versus placebo, and comparisons between the individual FX-322 groups (excluding the pooled FX-322 group). Odds ratios, their 95% CIs, and p-values will be reported.

- *Sensitivity Analyses of the Endpoint*

The analyses will be repeated for subjects in the PPAS.

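### The dB improvement flags are coded post-baseline minus baseline, so ears whose hearing worsened count as improved, and three composite endpoints inherit the reversal

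*SAP*

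**What the plan says.** Five SAP sections define an improvement flag on a dB scale.

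- **7.5.2** (air and bone conduction, two contiguous frequencies): the flag "for treated ears will be computed as 1 if the post-baseline threshold – baseline threshold is" at least 10 dB.
- **7.5.3** (air and bone conduction, any frequency): the flag is "computed as 1 if the post-baseline threshold – baseline threshold is" at least 15 dB.
- **7.6.2 and 7.6.3** (extended high frequency audiometry): the same two rules, with the same order of subtraction.
- **7.4.7** (median Spearman-Kärber estimate from WIN): the flag "will be computed as 1 if the post-baseline Spearman-Kärber estimate – baseline Spearman-Kärber estimate is ≥3 and as 0" otherwise.

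Three composites are built on these by cross-reference. Sections 7.5.4 and 7.6.4 combine the 10 dB and 15 dB flags. Section 7.5.9 pairs a word-score gain with a pure-tone criterion and states that "improvement in 2 contiguous frequencies for AC thresholds is defined in Section 7.5.2", with 7.5.3 supplying the 15 dB part.

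The SAP also fixes the direction of the pure-tone scale. Section 7.5 describes NR as "no response due to subject audiometric thresholds greater than the maximal calibrated dB of the equipment" and replaces a post-Screening NR by the site's equipment maximum plus 5 dB. The pure-tone and extended high frequency flags use these imputed values.

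**The concern.** A hearing threshold is the level needed to hear the tone, so a fall is a gain and a rise is a loss. Each flag is labelled improvement but is triggered by a rise. The label and the formula contradict each other, and the formula is what a programmer is asked to implement.

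Followed literally, the affected incidence tables and odds ratios would favour the arm whose hearing deteriorated. On these outputs a beneficial drug would look harmful and an ototoxic one effective. The flags could also contradict the protocol's own safety definition: Protocol Section 13 makes an asymmetric loss above 20 dB at one frequency in the treated ear an adverse event of special interest, and an air-conduction loss of that size at a frequency tested under 7.5.3 would be scored there as an improvement.

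**Working it through.** The plan gives no figure to reproduce here. The check applies the written rules to cases and compares them with baseline minus post-baseline.

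**Pure tones.** The inputs are the 10 dB and 15 dB rules, the eight air-conduction frequencies and the NR imputation, all from the SAP. The starting audiogram is an assumed illustration: 30, 35, 40, 50, 60, 65, 70 and 75 dB at 0.25, 0.5, 1, 2, 3, 4, 6 and 8 kHz. The NR row assumes an equipment maximum of 100 dB, so NR becomes 100 + 5 = 105 dB and the change is 105 − 75 = +30 dB. Entries are the flags under 7.5.2 / 7.5.3 / 7.5.4.

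| Change in the ear | As written | Baseline minus post-baseline |
|---|---|---|
| Gain of 10 dB at 6 and 8 kHz | 0 / 0 / 0 | 1 / 0 / 1 |
| Loss of 10 dB at 6 and 8 kHz | 1 / 0 / 1 | 0 / 0 / 0 |
| Gain of 15 dB at 8 kHz | 0 / 0 / 0 | 0 / 1 / 1 |
| Loss of 25 dB at 4 kHz | 0 / 1 / 1 | 0 / 0 / 0 |
| Loss of 15 dB at 3 and 4 kHz | 1 / 1 / 1 | 0 / 0 / 0 |
| 75 dB to NR at 8 kHz | 0 / 1 / 1 | 0 / 0 / 0 |

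Every loss is scored as an improvement and every gain as none, including the ear that went from a measurable threshold to no response.

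**Words-in-Noise.** SAP 7.4.6 gives an initial level of 24 dB, a step of 4 dB and 10 words per step, with the word term subtracted. With w words recognised out of 70, the median estimate is

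T = 24 + 0.5 × 4 − 4w/10 = 26 − 0.4w.

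It runs from 26.0 dB at w = 0 to −2.0 dB at w = 70, and each extra word lowers it by 0.4 dB. A 3 dB change is 3 / 0.4 = 7.5 words, so 8 whole words. From a baseline of w = 35 (T = 12.0 dB):

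| Words at follow-up | T (dB) | Post minus baseline (dB) | 7.4.7 as written | 7.4.7 reversed | 7.4.5 (at least 10%, 7 words) |
|---|---|---|---|---|---|
| 43 (+8) | 8.8 | −3.2 | 0 | 1 | 1 |
| 27 (−8) | 15.2 | +3.2 | 1 | 0 | 0 |

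Sections 7.4.5 and 7.4.7 therefore disagree about the same ear.

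**Composite 7.5.9.** The word-score half is correctly signed and the pure-tone half is not. An ear that gains on both scores 0. An ear that gains words and loses thresholds scores 1. An ear that loses on both scores 0.

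**Would the error show in the overall rates?** An illustrative simulation applied the air-conduction composite (7.5.4) to 100,000 ears per scenario. Its assumptions, none from the documents, are independent normal changes at eight frequencies, SD 4, 5 or 7 dB, rounding to 5 dB steps and one true shift common to all frequencies. Entries are for SD 4 / 5 / 7.

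| True change | Rate as written | Rate with sign reversed |
|---|---|---|
| None | 1.3% / 7.2% / 31.5% | 1.3% / 7.4% / 31.5% |
| 5 dB gain | 0.0% / 0.2% / 5.5% | 45.4% / 61.8% / 80.3% |
| 5 dB loss | 45.8% / 61.7% / 80.4% | 0.0% / 0.2% / 5.3% |

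With no true change the two codings give nearly the same rate, so a placebo rate would not give the error away. It appears only as a reversed treatment effect.

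**The case against.** The strongest objection is that the section titles make the intent plain and a competent programmer would code it correctly; table specifications are in separate documents. That may be so, but correct code would then depart from the SAP without record, while literal code would reverse the result. No SAP section defines a dB change the other way round, and Section 11 records no such change.

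Second, the study is exploratory. It has no single primary endpoint, its p-values are descriptive, and the GEE comparisons of these flags are optional. This limits the stakes. The incidence tables in 7.5.2 to 7.5.4 and 7.4.7 are firm commitments, however, as is the logistic regression in 7.5.9.

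Third, much of the plan is untouched, and this point stands. The mixed models for thresholds, pure tone average and the Spearman-Kärber estimate use dB values directly. The word-recognition and WIN percentage endpoints are correctly signed, the shift-from-no-signal flags in 7.6.6 to 7.6.8 use no subtraction, and hearing loss is tabulated separately as an adverse event of special interest. A reader could therefore notice the conflict, but the same report would contain contradictory tables.

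Fourth, two gaps outlast the sign change. NR at Screening stays missing, so an ear that moves from NR to a measurable threshold has no baseline at that frequency. The pure-tone and extended high frequency flags also assign 0 otherwise, without the non-missing condition found in 7.3.5, 7.4.5 and 7.4.7. Both are separate from this point.

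Finally, the symbols of the formula in 7.4.6 are partly garbled in the text available, so 26 − 0.4w is a reading of it. The subtracted word term and the constants are legible, and the pure-tone finding does not depend on it.

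**Conclusion.** The concern holds and must be fixed. The sign is reversed in five definitions (7.4.7, 7.5.2, 7.5.3, 7.6.2, 7.6.3) and carries into three composites (7.5.4, 7.6.4, 7.5.9). Within this group the reversal is complete: as written, a loss that reaches the cut-off scores 1 and an equal gain scores 0. For 7.5.9 the error is narrower, because a correctly signed word-score gain is still required.

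The pure-tone conclusion rests only on the SAP's own text. The WIN conclusion also rests on the reading of 7.4.6 given above. The simulated rates depend on assumed variability and show only the form the error would take. The affected outputs belong to the CSR, and those for pure tones, WIN and the 7.5.9 composite are also listed for the Day 90 interim analysis in SAP Section 10; extended high frequency audiometry is not listed there.

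**What to change.** Define improvement as baseline minus post-baseline in all five sections: at least 10 dB in 7.5.2 and 7.6.2, at least 15 dB in 7.5.3 and 7.6.3, and at least 3 dB in 7.4.7. The sign in 7.5.4, 7.5.9 and 7.6.4 is then corrected through the cross-references. State once, in 7.4.6, 7.5 and 7.6, that a lower dB value is better.

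Check the derivation code against the corrected text, with test cases such as those above, and rerun any interim outputs produced under the present rule. The cost is one line of wording in each of five sections, a sentence on direction in three and the matching code. No additional data are needed.

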### **8.4.2 Inclusion Criteria**

To be eligible for study entry subjects must satisfy all of the following criteria:

1. Subject has read and voluntarily signed the Informed Consent Form (ICF) after all questions have been answered and prior to any study-mandated procedure.
2. Adult aged 18-65 years inclusive.
3. Established diagnosis of stable sensorineural hearing loss by standard audiometric measures for  $\geq 6$  months prior to the Screening visit (no changes in air conduction greater than 10 dB at a single frequency or greater than 5dB at two contiguous frequencies from the prior audiogram to the Screening audiogram in the study ear).
4. Documented medical history consistent with hearing loss being caused by noise exposure or sudden sensorineural hearing loss (documented audiogram at least 6 months prior to screening required).
5. A pure tone average of 26-70 dB at 500Hz, 1000Hz, 2000Hz, and 4000Hz in the ear to be injected.
6. Subjects with a 15% - 85% correct score on Word Recognition test (8 – 42 words correct out of 50) at Screening in the study ear.
7. Ability to communicate well with the Investigator and is willing to comply with and complete all the study procedures.
8. Female subjects must be of non-childbearing potential or will need to utilize two methods of highly effective contraception during the study participation (e.g. hormonal contraception or an intrauterine device and condoms) or remain abstinent. Male subjects

should use condoms with spermicide during the course of the study or remain abstinent. Subjects should not donate sperm or ova during the study period.

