#### **14.1.5 Efficacy Exploration**

Efficacy endpoints will be summarized descriptively at each study timepoint including baseline. Calculations will include the observed data at each timepoint, and if relevant, the change from baseline. For continuous endpoints means, medians, standard deviations, minimums and maximum will be provided. For categorical endpoints the number and percent of subjects within each category will be calculated. Tabulations for selected endpoints will be presented by subgroups such as age, study site, duration of hearing loss, smoking status, and stratification factors used at randomization. Details will be provided in the SAP. For descriptive analyses, subjects with missing data will be excluded for a particular calculation.

For questionnaires, the analysis will follow the instructions for scoring and handling of missing data appropriate for the particular instrument.

Inferential statistical methods examining continuous endpoints will be examined via a Mixed Model for Repeated Measures (MMRM). Analyses will include pairwise contrasts and dose response. Inferential analyses for categorical endpoints will be analysed using univariate methods and/or Generalized Linear Mixed Models (GLMM). When appropriate, models will include adjustments for baseline as well as the stratification factors used at randomization. Departures of these models from the statistical assumptions will be assessed and alternative approaches maybe employed. Additionally, univariate models such as Analysis of Covariance and/or count models examining single timepoints of interest may also be examined. General methods for handling missing data for inferential analyses are described below (Section 14.2).

The inferential analyses will not be adjusted for multiple endpoints; however, for a given endpoint, adjusted p-values for pairwise comparisons to a control will be provided where

relevant along with the unadjusted p-values. Unadjusted 95% confidence intervals will also be provided. In some circumstances, adjusted confidence intervals may be calculated.

Efficacy endpoints will be analysed using the FAS. Further details regarding the exploratory analysis of efficacy will be outlined in the SAP.

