## 11. CHANGES TO THE ANALYSES PLANNED IN THE PROTOCOL

Protocol Section 14.1.5 specifies that adjusted p-values and confidence intervals may be computed for pairwise treatment comparisons for a given endpoint. Such adjusted analyses are no longer planned in the SAP and there will be no adjustments for multiplicity of group comparisons.

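### The SAP's dB responder rules subtract the wrong way round, and leaving no-response missing at Screening stops a regained frequency from counting even after the sign is corrected

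*SAP*

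**What the plan says.** **Responder rules.** SAP 7.5.2 (10 dB at two contiguous frequencies) and 7.5.3 (15 dB at any frequency) cover air and bone conduction; 7.6.2 and 7.6.3 repeat them for extended high frequency audiometry (EHFA). Each indicator is "computed as 1 if the post-baseline threshold – baseline threshold is" at or above the cut-off, and 0 in every other case.

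**Sections that reuse them.** The composites in 7.5.4 and 7.6.4 refer back to these rules. So does the composite of word scores and audiometry in 7.5.9: "improvement in 2 contiguous frequencies for AC thresholds is defined in Section 7.5.2 and post-baseline" 15 dB improvement by 7.5.3.

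**Direction of the scale.** SAP 7.5 describes NR as "no response due to subject audiometric thresholds greater than the maximal calibrated dB of the equipment". A higher threshold is therefore worse.

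**NR.** For measurements after Screening, NR is "imputed using the maximum dB for the audiometry equipment of a given site plus 5 dB and classified as no signal at that frequency". For the visit that supplies the baseline the rule is "Missing response values at Screening will remain missing". SAP 7.6 has the same pair of rules.

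**Words in noise.** SAP 7.4.7 scores improvement when the post-baseline median Spearman-Kärber estimate minus the baseline estimate is at least 3 dB.

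**The concern.** A responder table headed improvement would count ears that lost hearing and leave out ears that gained it. In 7.5.9 the word-score limb has the right sign (7.3.5 and 7.4.5), so the composite as written asks for better word scores together with a worse air-conduction threshold at some frequency or pair.

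The rules also collide with the safety definitions. Protocol Section 13 makes an asymmetric loss of more than 10 dB at two adjacent frequencies an adverse event of special interest. A 15 dB loss at two adjacent frequencies could be reported both as such an event and as an improvement.

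A programmer may correct the sign without comment because the headings say improvement. The NR asymmetry would survive that. It removes the change from no measurable hearing to measurable hearing, which a restorative treatment would hope to show. SAP Section 10 puts the pure tone audiometry and composite outputs in the planned Day 90 interim analysis, so both faults would reach those tables as well as the final report.

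**Working it through.** The documents give no responder rate or power figure to reproduce. The check applies the rules to worked cases.

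**1. Single frequency, 15 dB rule.** Assumed site maximum M = 100 dB, so NR = M + 5 = 105 dB after Screening.

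| Screening to later | As written: post − baseline | Score as written | Score, sign corrected only | Score, sign corrected and Screening NR = 105 |
|---|---|---|---|---|
| 60 to 45 | −15 | 0 | 1 | 1 |
| 45 to 60 | +15 | 1 | 0 | 0 |
| NR to 85 | no baseline | not 1 | not 1 | 1 (105 − 85 = 20) |
| 85 to NR | 105 − 85 = +20 | 1 | 0 | 0 |
| NR to 95 | no baseline | not 1 | not 1 | 0 (105 − 95 = 10) |

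Where there is no baseline, the frequency is 0 or missing depending on how the rule is read; it is never 1. As written, a loss to NR scores 1 when M + 5 − baseline ≥ 15, that is, when baseline is at or below M − 10.

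**2. Pair, 10 dB rule.** 6 kHz goes from 90 to 80 dB and 8 kHz from NR to 95 dB. As written the differences are −10 and missing: not met. With the sign corrected they are +10 and missing: not met. With both corrections they are +10 and 105 − 95 = +10: met.

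**3. Words in noise (7.4.7).** The formula in 7.4.6 is damaged in the public text, but its structure and inputs can be read: start 24 dB, step 4 dB, 10 words per step, percentile 0.5.
- 35 words: 24 + 0.5 × 4 − 4 × 35/10 = 12.0 dB
- 43 words: 24 + 0.5 × 4 − 4 × 43/10 = 8.8 dB

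Post minus baseline is −3.2 dB. This is a gain of 3.2 dB, above the 3 dB cut-off, and it scores 0.

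**4. Where Screening NR can arise.** Protocol 8.4.2 requires "A pure tone average of 26-70 dB at 500Hz, 1000Hz, 2000Hz, and 4000Hz in the ear to be injected". NR is therefore most likely at EHFA and at the standard air frequencies outside that average (0.25, 3, 6 and 8 kHz). It is less likely at 0.5, 1, 2 or 4 kHz but not excluded, because the protocol does not say how NR enters the eligibility average. Carried as 105 dB, an ear with 40, 40, 40 and NR averages (40 + 40 + 40 + 105)/4 = 56.25 dB and is eligible.

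**5. Illustrative effect of the sign alone on the 7.5.4 air-conduction rate.** Assumptions, none from the documents: eight frequencies, independent normal changes rounded to 5 dB, and a true 10 dB gain at 6 and 8 kHz.

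| SD of change | No true change, as written / corrected | True gain, as written | True gain, sign corrected |
|---|---|---|---|
| 3 dB | 0.0% / 0.0% | 0.0% | 71.9% |
| 5 dB | 7.2% / 7.3% | 5.4% | 69.3% |
| 7 dB | 31.6% / 31.6% | 24.8% | 75.8% |

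The levels depend on the assumed SD. The direction does not: as written, benefit never raises the rate.

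**6. Missing visits.** SAP Section 3 gives missing categorical data their own row and leaves them out of percentages. SAP 7.1.6 plans no formal imputation. The word-score rules in 7.3.5, 7.4.5 and 7.4.7 carry a non-missing condition; the four audiometry rules do not, and they score 0 in every other case. Protocol 10.1.5, 10.1.6 and 10.1.8 allow a phone call to replace the Day 60, 90 or 150 clinic visit. The two sets of wording conflict.

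**The case against.** The best defence is that the headings make the intent plain, the responder models in these sections are optional, SAP 7.2 names no single primary endpoint and SAP 7.1.4 calls all p-values descriptive. That limits the consequence. It does not make the definitions right, and the responder counts and the 7.5.9 logistic model are not optional.

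Second, a regained frequency is not lost everywhere. An ear with NR at one frequency can still qualify through others, and 7.6.6 to 7.6.8 credit EHFA recovery. Both points stand, but the second is descriptive only and has no counterpart in standard audiometry, which feeds 7.5.9. Those sections speak of a missing or imputed response at baseline, which might suggest that Screening NR is imputed; 7.5 and 7.6 say it is not.

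Four stronger readings are tempting and not supported:
- *All the audiometry comparisons are compromised.* The mixed models in 7.5.1 and 7.6.1 analyse the thresholds themselves. They use no reversed difference, and a regained threshold enters at its measured value.
- *The entry average confines NR to a fixed set of frequencies.* Step 4 shows that it does not.
- *A visit without audiometry will be scored 0.* The general missing-data rules point the other way, so this is a conflict to settle.
- *The composite requires hearing to worsen overall.* One frequency or pair is enough, and others may improve.

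**Conclusion.** The sign is wrong as written in five sections (7.5.2, 7.5.3, 7.6.2, 7.6.3 and 7.4.7), and 7.5.4, 7.6.4 and the audiometry limb of 7.5.9 inherit it. This follows from the text alone and needs no assumption. Taken literally, those results run opposite to their label.

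The NR asymmetry also follows from the text. Its size is unknown, because the documents give neither an NR rate nor equipment limits; the 100 dB maximum and the simulated rates are illustrations. The missing-visit wording needs clarification only.

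This should be fixed. It does not undermine the mixed-model analyses of thresholds, and a reader should not infer that the trial's audiometry as a whole is uninterpretable.

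**What to change.** 1. Define improvement as baseline minus post-baseline in 7.5.2, 7.5.3, 7.6.2, 7.6.3 and 7.4.7. The composites then follow by reference.
2. Set recorded NR to the site maximum plus 5 dB, flagged as no signal, at every visit including Screening. Keep tests that were not done as missing.
3. Add a non-missing condition to the four audiometry rules, so that a visit without audiometry is missing and not 0. State how 7.5.9 treats a missing Day 90 or Day 210.

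Changes 1 and 2 are both needed for a regained frequency to count.

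The cost is SAP wording and derivation code. No new data are needed, because SAP 7.1.6 already tabulates NR and not done separately. The drawback is a single imputed value for a censored baseline, which the SAP already accepts after Screening. A regained frequency would then count only if measured at or below the maximum minus 5 dB (10 dB rule) or the maximum minus 10 dB (15 dB rule).
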